4.1. Intended Use and Study Population

The IUP for this test is adults of either sex, 45 years or older, who are at average-risk for CRC. The study population were adults of either sex ages 45-85, referred by a healthcare professional for CRC screening. Typical subjects presented for medical intervention in a health care setting and met CRC screening criteria for a CS. High-risk individuals and individuals with gastrointestinal symptoms warranting diagnostic or surveillance CS were ineligible. Subjects were considered enrolled after a determination was made by the Investigator that the subject was eligible to participate according to the inclusion/exclusion criteria and understood and signed the informed consent form. No waivers of inclusion or exclusion criteria were granted by the Investigator in this study. Study sites consisted of mostly gastroenterology specialty practice and general health care sites.

4.2. Inclusion and Exclusion Criteria

Inclusion Criteria

For enrollment to this study, subjects met all the following criteria:

This document contains confidential, proprietary information and may not be reproduced or disclosed in whole or in part without written authorization from Freenome Holdings, Inc

		Approval Status	Approved
		Effective Date	5-Jan-2024
Document Number	PL-00052	Current Revision	5
Document Title	Clinical Validation of Freenome's Methylation Blood Test for the Early Detection...		
Document Category	Plan		

1. 45-85 years of age (inclusive) within 30 days of enrollment (target ≥ 70% of subjects to be 65-85).
2. Willing to undergo a SOC CS within 90 days of blood collection.
3. Considered by a physician or healthcare provider to be “average-risk” for CRC.
4. Able and willing to provide blood samples per protocol.
5. Able to comprehend and willing to sign and date the written informed consent document(s).

Exclusion Criteria

Subjects were excluded from enrolling into the study if any of the following were met:

1. Family history
 - 1.1. At least one (1) first-degree relative diagnosed with CRC before the age of 60 (Note: First degree relatives include parents, siblings, and offspring).
 - 1.2. At least two (2) first-degree relatives diagnosed with CRC at any age.
 - 1.3. Known hereditary gastrointestinal cancer syndrome including but limited to the following:
 - Hereditary non-polyposis CRC syndrome or Lynch Syndrome
 - Familial adenomatous polyposis
 - Cowden's Syndrome
 - Juvenile Polyposis Syndrome
 - MUTYH-associated Polyposis
 - Peutz-Jeghers Syndrome
 - Serrated Polyposis Syndrome
2. Personal history
 - 2.1. CRC or colorectal adenoma
 - 2.2. History of malignancy (except for non-melanomatous skin cancer) at the time of enrollment, and for the 5 years preceding enrollment
 - 2.3. IBD, including chronic ulcerative colitis and Crohn's disease
 - 2.4. Total colonic resection
 - 2.5. Cystic fibrosis
 - 2.6. CS in the 9 years preceding enrollment with the exception of an incomplete colonoscopy, or for a poor or inadequate bowel prep
 - 2.7. Sigmoidoscopy or CT colonography in the 4 years preceding enrollment
 - 2.8. Stool DNA testing in the 2 years preceding enrollment
 - 2.9. Fecal occult blood testing or fecal immunochemical testing in the 6 months preceding enrollment

This document contains confidential, proprietary information and may not be reproduced or disclosed in whole or in part without written authorization from Freenome Holdings, Inc

		Approval Status	Approved
		Effective Date	5-Jan-2024
Document Number	PL-00052	Current Revision	5
Document Title	Clinical Validation of Freenome's Methylation Blood Test for the Early Detection...		
Document Category	Plan		

- 2.10. Requiring an immediate or emergent colonoscopy for the investigation of symptoms
- 2.11. Solid organ or bone marrow transplantation
- 2.12. Blood product transfusion in the 120 days preceding enrollment
- 2.13. Any trauma or surgery requiring overnight inpatient hospitalization in the 30 days preceding enrollment
- 3. A medical condition which, in the opinion of the investigator, should preclude enrollment into the study.
- 4. Participated or currently participating in a clinical research study in which an experimental medication has been administered during the 60 days leading up to and including the date of providing informed consent or may be administered through the time of the CS.
- 5. Known to be pregnant.

4.3. Blood collection

After meeting eligibility and completing consent, subjects had the option to have blood collection completed either at the study site or via mobile phlebotomy services, in which case the subject could have blood collected in their home or at another location of preference. In cases where blood collection was not successful, a redraw was allowable as long as the subject had not yet completed colonoscopy.

The blood samples were received from the courier and inspected to ensure they were in acceptable condition. A sample was failed and rejected or placed on hold if the specific failure or hold criteria were met. Lab personnel then conducted sample accessioning in the Simple Laboratory Information Management System. The plasma and buffy coat were isolated from whole blood using the automated easyBlood and STAR system on the Hamilton Microlab in the Freenome Clinical Laboratory. The isolated plasma was aliquoted and stored at -80°C. The samples are maintained in freezer units located in the limited badge access clinical laboratory.

4.4. Colonoscopy

Subjects underwent a SOC bowel preparation followed by SOC screening colonoscopy within 90 days of blood collection (to ensure CRC status has not changed between blood draw and CS). Steps were taken to ensure quality of bowel preparation and colonoscopy were sufficient to evaluate the presence or absence of ACN. In cases where a non-ACN subject did not meet adequate quality colonoscopy, a repeat colonoscopy was allowable within 90 days of blood

This document contains confidential, proprietary information and may not be reproduced or disclosed in whole or in part without written authorization from Freenome Holdings, Inc

		Approval Status	Approved
		Effective Date	5-Jan-2024
Document Number	PL-00052	Current Revision	5
Document Title	Clinical Validation of Freenome's Methylation Blood Test for the Early Detection...		
Document Category	Plan		

collection. Due to the impact that COVID-19 had during this study, sites were occasionally given waivers for completing CS within 120 days after the blood collection. All subjects were required to provide a colonoscopy report, and additionally where applicable, histopathology reports, imaging reports, or operative notes on cancer staging. Although no long-term follow-up is planned, subjects may also be contacted by site personnel for up to 3 years following the completion of the study to gather additional information (e.g., any new cancer diagnosis).

A non-ACN subject who had a bowel preparation rated as less than fair (i.e. poor or inadequate), or an incomplete CS, was considered unevaluable and therefore will be excluded from analysis of all primary and secondary endpoints. An ACN subject who had a bowel preparation rated as less than fair or had an incomplete CS will be included in the analyses. Poor bowel preparation was defined as semisolid stool that could not be suctioned or washed away and < 90% of mucosa was seen. Inadequate bowel preparation was defined as needing repeat preparation for screening. A complete CS was defined as reaching the cecum (reaching the junction between the small and large intestine if the cecum has been resected) or reaching the neo-cecum. Cecal intubation was documented by photographic evidence and/or documentation of cecal intubation.

4.5. Data collection

All subjects were assessed for eligibility and consented. Blood specimens were collected prior to bowel preparation for screening CS. Baseline information (e.g., demographic, lifestyle and concomitant medication, etc.) was collected. All subjects also provided a CS report. Any positive CS required follow-up data collection, including but not limited to, the CS report, the associated histopathology report if any lesions were biopsied or removed, the surgical pathology report if any surgery was performed to remove lesions identified during the CS, and any other reports (e.g., imaging reports) required to determine the tumor-node-metastasis stage (based on the American Joint Committee on Cancer Staging Manual, 8th edition).

4.6. Central Pathology Review

Subjects will have their clinical outcome determined by using the best available evidence of their disease state. The most clinically significant lesion (clinical significance is defined in rank order in Table 3) among synchronous lesions is defined as the index lesion. All CS reports, as well as local histopathology reports when applicable, were reviewed by a central pathologist (Tier 1) to categorize the histopathological categories of the index lesion (i.e., CRC, AA, NAA, and NEG), as per histopathological categories defined in the protocol as well as in detailed work

This document contains confidential, proprietary information and may not be reproduced or disclosed in whole or in part without written authorization from Freenome Holdings, Inc

		Approval Status	Approved
		Effective Date	5-Jan-2024
Document Number	PL-00052	Current Revision	5
Document Title	Clinical Validation of Freenome's Methylation Blood Test for the Early Detection...		
Document Category	Plan		

instructions for pathology review (Table 3). Cases that were categorized as CRC or as certain subtypes of AA (AA2.1, AA2.2, AA2.4, and AA2.5), and a subset comprising 5% of all NEG4.1 (the first NEG4.1 from each site, then every 20th NEG4.1 per site after that), were additionally assessed as a Tier 2 independent central pathology review of tissue samples (i.e. H&E slides, fixed tissue blocks, or digital images). Any inconsistency between the site-reported Tier 1 assessments and the central pathologist Tier 2 assessment triggered an adjudication by a third independent central pathologist to break the tie (Tier 3).

Table 3 - Histopathological categories and definitions, including subtype definitions for AA, NAA, and NEG

Cat.	Definition for Central Pathology Review	Definition for Statistical Analysis
1	Colorectal cancer (CRC), all stages (I-IV)	Colorectal cancer (CRC), all stages (I-IV)
2	Advanced adenoma (AA), including: 
 2.1. Adenoma with carcinoma in situ or high-grade dysplasia, any size 2.2. Adenoma, villous growth pattern ($\geq 25\%$), any size 2.3. Adenoma ≥ 1.0 cm in size 2.4. Sessile serrated adenoma/polyp (SSA/P) with or without cytological dysplasia ≥ 1.0 cm and hyperplastic polyps (HP) ≥ 1.0 cm. 2.5. Traditional serrated adenoma (TSA), any size 	Advanced adenoma (AA), including: 
 2.1. Adenoma with carcinoma in situ or high-grade dysplasia, any size 2.2. Adenoma, villous growth pattern ($\geq 25\%$), any size 2.3. Adenoma ≥ 1.0 cm in size 2.4. Sessile serrated adenoma/polyp (SSA/P) with or without cytological dysplasia ≥ 1.0 cm 2.5. Traditional serrated adenoma (TSA), any size
3	Non-advanced adenoma (NAA)	Non-advanced adenoma (NAA)

This document contains confidential, proprietary information and may not be reproduced or disclosed in whole or in part without written authorization from Freenome Holdings, Inc

		Approval Status	Approved
		Effective Date	5-Jan-2024
Document Number	PL-00052	Current Revision	5
Document Title	Clinical Validation of Freenome's Methylation Blood Test for the Early Detection...		
Document Category	Plan		

[figure not shown]
Cat.	Definition for Central Pathology Review	Definition for Statistical Analysis
	3.1. ≥ 5 adenomas, all < 1.0 cm in size, non-advanced 3.2. 1 to <5 adenomas, all < 1.0 cm in size, non-advanced	3.1. ≥ 5 adenomas, all < 1.0 cm in size, non-advanced 3.2. 1 to <5 adenomas, all < 1.0 cm in size, non-advanced 3.3. HP ≥ 1.0 cm
4	Negative (NEG) 4.1. All SSA/P < 1.0 cm, and HP < 1.0 cm not in sigmoid or rectum 4.2. HP < 1.0 cm in the sigmoid or rectum 4.3. Negative upon histopathological review 4.4. No findings on colonoscopy, no histopathological review	Negative (NEG) 4.1. All SSA/P < 1.0 cm, and HP < 1.0 cm not in sigmoid or rectum 4.2. HP < 1.0 cm in the sigmoid or rectum 4.3. Negative upon histopathological review 4.4. No findings on colonoscopy, no histopathological review

4.7. Subject Disposition

The disposition of the subjects in this study is illustrated in the flowchart below (Figure 4), indicating the numbers reaching each stage and those excluded from the full analysis set in the study at that stage with a summary count for each of the major reasons for not proceeding. Sponsor is defining “all enrolled subjects” as subjects enrolled in the study. Sponsor is defining “enrolled*” subjects as those enrolled on or after April 5, 2021, and only those subjects will be included in the analysis set.

This document contains confidential, proprietary information and may not be reproduced or disclosed in whole or in part without written authorization from Freenome Holdings, Inc

		Approval Status	Approved
		Effective Date	5-Jan-2024
Document Number	PL-00052	Current Revision	5
Document Title	Clinical Validation of Freenome's Methylation Blood Test for the Early Detection...		
Document Category	Plan		

*Enrolled Subjects are defined as subjects enrolled on or after April 5, 2021; **SAS Subjects are defined as subjects with an attempted blood sample collection.

Figure 4 - Subject Disposition Flowchart

A subject may be discontinued and therefore excluded from all primary and secondary analyses due to the following reasons:

- Withdrawal by subject
- Physician decision
- Subject or Trial site terminated by Sponsor
- Adverse event
- Death
- Protocol deviation (refer to next section)

This document contains confidential, proprietary information and may not be reproduced or disclosed in whole or in part without written authorization from Freenome Holdings, Inc

		Approval Status	Approved
		Effective Date	5-Jan-2024
Document Number	PL-00052	Current Revision	5
Document Title	Clinical Validation of Freenome's Methylation Blood Test for the Early Detection...		
Document Category	Plan		

- Blood sample failure (e.g., resulting from errors in labeling, improper collection or handling, poor specimen quality, assay-related failures)
- Unevaluable patient due to CS (e.g., patient with only unevaluable colonoscopies, defined as incomplete CS or bowel preparation quality rated as poor or inadequate (unless diagnosed with CRC or AA))
- Other

4.8. Protocol Deviations

Protocol deviations and actions taken to resolve the deviations were noted on the designated source documents at each clinical site and described in study monitoring reports. Determination of whether a protocol deviation results in a subject being ineligible for final analysis will be reviewed on a case-by-case basis. All protocol deviations will be described in the final study report from the following categories.

- Consent related
- Inclusion/Exclusion Criteria related
- Blood Draw related
- Colonoscopy related

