### **7.1 Evaluable Status**

A subject may be considered unevaluable and therefore excluded from all primary and secondary analyses if any of the following criteria are met: (Note this list is not exhaustive. Refer to the SAP for details.)

- No Freenome test result (for example, resulting from errors in labeling, improper collection or handling, and poor specimen quality)
- Missing any of the required reports, i.e. CS and, if applicable, histopathology and imaging reports
- Incomplete CS, or no photographic evidence or documentation of cecal intubation (unless diagnosed with CRC)
- Bowel preparation quality rated as poor or inadequate (unless diagnosed with CRC)
- Subjects found to have occult IBD on CS

Unevaluable subjects will be assessed for bias as described in the SAP.

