Another impact the pandemic had on the study was the extended storage of blood samples. The slower than expected initial enrollment and the increased enrollment target caused by the lower assumed CRC prevalence required the Sponsor to extend the enrollment period for the study. As a result, samples were stored considerably longer than originally planned. The PREEMPT CRC samples will begin processing around July 2023. Using the April 5, 2021 (inclusive) cutoff date for the analysis population reduces the real-time plasma stability data needed to 27 months. In order to include samples from date of first enrollment, in May 2020, real-time plasma stability data would be needed for 39 months.

The clinical validation of the FMBT-CRC will be based on PREEMPT CRC samples from participants enrolled on or after April 5, 2021, due to the fact that subjects enrolled prior to this date were less likely to represent the IUP and it would be unlikely that the unmeasured factors could be accounted for in analysis. This population, which enrolled after vaccines allowed improved access to healthcare, had a CRC incidence rate more in line with epidemiological predictions. Revised power calculations, using the revised enrollment window, show that the study is still overpowered for estimating the primary and secondary endpoints with a high degree of confidence.

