4.9. Blinding

The PREEMPT CRC study is a blinded study and follows blinding as per the study blinding plans. For this study, blinding is defined as preventing knowledge of subject-specific histopathological classifications or blood test results that could bias the study. Blood specimens were de-identified prior to being sent to Freenome for processing and storage. Specimen testing will be performed by laboratory personnel blinded to the results of the SOC screening colonoscopy. Subjects, their health care providers, and investigators will remain blinded to the results of FMBT-CRC.

To minimize risk of unintended unblinding at the time of data analysis, the study also maintained an unblinding plan which outline the Sponsor-level processes for unblinding specific roles/data, such as data preparation, data quality and control, and data analyses, as needed through

This document contains confidential, proprietary information and may not be reproduced or disclosed in whole or in part without written authorization from Freenome Holdings, Inc

		Approval Status	Approved
		Effective Date	5-Jan-2024
Document Number	PL-00052	Current Revision	5
Document Title	Clinical Validation of Freenome's Methylation Blood Test for the Early Detection...		
Document Category	Plan		

completion of this study (PL-00071). Unblinded roles are limited to a need-basis. Clinical Data Manager(s), Clinical Scientist(s), and Biostatisticians(s) can be unblinded if their defined responsibilities need to be conducted. Individuals granted access to unblinded data will not communicate results or characteristics of the unblinded data in any way that would expose information on subject-specific histopathological classifications (or any other blinded content) to individuals not granted access. Individuals granted access to the blinded data must not work on the classifier algorithms or have access to results of the blood test prior to study database lock. Individuals granted access to blinded data will be documented. The Sponsor will decide on the level of unblinding of PREEMPT CRC blinded data at the end of study.

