5.3. Full Analysis Set (FAS)

This set will include those subjects enrolled on or after April 5, 2021, who met eligibility criteria, consented, and have an evaluable Freenome test result, with confirmed diagnosis from the colonoscopy and best available evidence of histopathology, including central pathology review.

This will be the population used in the analyses of the primary and other endpoints.

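### Does case-by-case review of protocol deviations leave the set of colorectal cancer cases behind the primary sensitivity estimate open?

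*SAP*

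**What the plan says.** SAP Section 5.3 applies the April 2021 enrolment cutoff and admits to the FAS people "who met eligibility criteria, consented, and have an evaluable Freenome test result, with confirmed diagnosis from the colonoscopy", backed by histopathology. It adds: "This will be the population used in the analyses of the primary and other endpoints". Section 6.4 computes sensitivity for colorectal cancer (CRC) from all FAS subjects identified as CRC.

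Section 4.7 describes who drops out before the FAS. Its flowchart is said to show the numbers excluded from the FAS at each stage, with the main reasons. The text then reads: "A subject may be discontinued and therefore excluded from all primary and secondary analyses due to the following reasons". The list includes withdrawal, physician decision, termination by the sponsor, protocol deviation, blood sample failure, unevaluable colonoscopy and an open last item, Other. The deviation item points to Section 4.8, which leaves the decision to individual review: "Determination of whether a protocol deviation results in a subject being ineligible for final analysis will be reviewed on a case-by-case basis". Four categories are named there for reporting: consent, eligibility, blood draw and colonoscopy.

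Protocol Section 7.1 gives its own list of reasons for being unevaluable and defers to the SAP: "Note this list is not exhaustive. Refer to the SAP for details".

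On blinding, SAP Section 4.9 says that people given access to the blinded data must not work on the classifier or "have access to results of the blood test prior to study database lock". It cites a separate unblinding plan, PL-00071, which is not among the documents.

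**The concern.** Read alone, Section 5.3 is a closed definition. Read with Sections 4.7 and 4.8, it appears to have an exit that depends on judgement. A subject with CRC, a valid result and a blood-draw irregularity meets every condition in 5.3, yet could be removed under 4.8. No criterion, decision-maker or deadline is given. Section 4.9 protects the decision only if it is taken before database lock, and the visible text does not say that it is.

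This matters more for CRC sensitivity than for any other endpoint. It is co-primary, its lower bound must exceed 65%, and it rests on a planned minimum of 56 cases. Near the critical count, one subject decides whether the study succeeds. If removals could follow sight of the results, the one-sided 2.5% level would no longer be guaranteed.

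The tense of 4.8 seems to add to this. The revision effective 5 January 2024 still puts the review in the future, while sample processing was planned from about July 2023.

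**Working it through.** **Inputs.** SAP Section 7.1: 56 CRC cases, null 65.0%, assumed sensitivity 85.0%, at least 44 positives needed, lower bound 66.2%. Section 6.4: two-sided 95% Wilson interval, one-sided level 0.025. Section 7: mean CRC prevalence 3.264/(3.264 + 816.77) = 0.398%, which over 19,000 FAS subjects gives 75.6, or about 76 cases. The documents do not give the number of CRC subjects with a deviation, so numbers removed are assumptions.

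**Formula.** With p = x/n and z = 1.96, the Wilson lower bound is [p + z²/(2n) − z√(p(1−p)/n + z²/(4n²))] / (1 + z²/n).

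**The plan's figure.** 44/56 gives 66.18%, matching the stated 66.2%. 43/56 gives 64.23%, so 44 is the smallest passing count. The exact binomial probability of at least 44 of 56 is 2.04% at a true 65% and 93.2% at 85%.

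**Effect of removing test-negative cases.**

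| Before | Lower bound | After | Lower bound |
|---|---|---|---|
| 43/56 | 64.2%, fails | 43/55 | 65.6%, passes |
| 42/56 | 62.3%, fails | 42/54 | 65.06%, passes |
| 57/76 | 64.2%, fails | 57/75 | 65.2%, passes |

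**Worst case: results known and only test-negatives removed.** Success is declared if x/(n − j) passes for any j from 0 to k. At a true 65% and n = 56:

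- k = 0: P(X ≥ 44) = 2.04%
- k = 1: P(X ≥ 43) = 2.04% + 2.02% = 4.06%
- k = 2: P(X ≥ 42) = 4.06% + 3.33% = 7.39%

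With 76 cases the rate goes from 2.3% to 4.1% for k = 1.

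**How far the ceiling depends on removable cases existing.** The figures above assume that each test-negative case needed has a usable deviation. Suppose instead that each test-negative CRC case has one with probability q, still with results known and always exploited:

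| q (assumed) | 56 cases | 76 cases |
|---|---|---|
| 1% | 2.3% | 2.6% |
| 2% | 2.6% | 2.9% |
| 5% | 3.6% | 3.7% |
| 10% | 5.3% | 5.5% |

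**Exclusion without the result.** Removing k cases regardless of test result leaves a binomial sample of n − k with its own critical count. At a true 65%, k = 1, 2, 3 gives 2.5%, 3.1% and 1.8% from 56 cases, and 2.8%, 1.8% and 2.2% from 76. The rates go up and down with the discrete critical count and do not drift with k.

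**At the planned sensitivity.** At a true 85%, the chance of falling exactly one positive short is 96.6% − 93.2% = 3.4% with 56 cases, and 0.8% with 76.

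**What discretion remains for a CRC case with a valid result.**

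- *Consent and eligibility.* These are already FAS conditions in 5.3, and they are two of the four deviation categories.
- *Poor preparation or incomplete colonoscopy.* Section 4.4 expressly keeps subjects with advanced neoplasia, and 4.7 repeats the exception for CRC.
- *Colonoscopy at 91 to 120 days.* Section 4.4 reports waivers, and 8.4 analyses these subjects as an FAS subgroup, so they are in.
- *Labelling, handling, specimen and assay failures.* They have their own item in 4.7 and generally leave no evaluable result.
- *Physician decision.* Investigators and providers stay blinded to the test (4.9), so the decision cannot follow the result.

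Residual blood-draw and colonoscopy deviations and the Other item are left, together with sponsor termination, which has little scope once blood and colonoscopy are complete.

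**The tense argument.** Section 4 of the same revision also says: "The PREEMPT CRC samples will begin processing around July 2023". A document effective in January 2024 that puts July 2023 in the future cannot be used to date events by its verb tense. The change tables list an edit to 4.8 in Rev 3 and none in Rev 4 or Rev 5, so the sentence looks carried over.

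**The case for a change.** The strongest reply is that Section 4.9 separates diagnoses from results only until lock. Nothing visible says the deviation review is finished by then, and the existing safeguards act after the fact. Section 8.7 accounts for every Enrolled* subject, but its demographic comparisons cover enrolment before the cutoff, missing or incomplete colonoscopy, and missing test results, not deviation exclusions. The protocol's robustness analysis (Section 7.3.1) imputes missing elements, and a subject excluded for a deviation may have none. A short list of excluding deviations and a stated freeze date would cost almost nothing.

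Much of this is true as description. The visible text gives neither criteria nor a deadline, and the critical count is tight. It does not follow that the plan produces a wrong result. Section 8.7 requires the reason for each exclusion from the FAS, so a CRC case removed for a deviation would be visible and could be added back by any reader. PL-00071 covers unblinding for data preparation and analysis roles and may already fix the timing; both it and the disposition flowchart are unavailable here, so their silence cannot be assumed. A rule keeping every unlisted deviation in the FAS would also force unforeseen serious blood-draw errors into the primary analysis. That trades one risk for another. A supportive table with the excluded cases restored would not alter the primary result.

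**Conclusion.** The wording is loose, but no change to the plan is needed. Sections 4.7 and 5.3 are compatible once 4.7 is read as describing the route into the FAS, and the open discretion for a confirmed CRC case with a valid result is narrow.

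The possible harm at 56 cases is a false-success rate of at most 4.1% or 7.4%, against 2.0% with no removals and a planned 2.5%. To reach it, someone would have to hold both diagnosis and test result, test-negative cancers with a usable deviation would have to exist, and removal would have to be opportunistic. Section 4.9 blocks the first condition until lock. Without knowledge of results, no systematic bias is expected.

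This conclusion assumes that deviation decisions are closed by database lock, as is ordinary practice and as PL-00071 may specify. If decisions were in fact made after results were linked to diagnoses, that would be a conduct problem to examine through the Section 8.7 accounting.
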